10.2 Secondary Efficacy Parameters

There are four secondary efficacy parameters, which are all defined for the last 6 weeks of the 12-week Treatment Period, as follows:

- **Nausea responder:** a study participant is considered a nausea responder for the study if he/she has an improvement of ≥ 2 -points in the weekly nausea symptom score for each of the last 6 weeks during the 12-week Treatment Period.
- **Abdominal pain responder:** a study participant is considered an abdominal pain responder for the study if he/she has an improvement of ≥ 2 -points in the weekly abdominal pain symptom score for each of the last 6 weeks during the 12-week Treatment Period.
- **Bloating responder:** a study participant is considered a bloating responder for the study if he/she has an improvement of ≥ 2 -points in the weekly bloating symptom score for each of the last 6 weeks during the 12-week Treatment Period.
- **Postprandial fullness responder:** a study participant is considered a postprandial fullness responder for the study if he/she has improvement of ≥ 2 -points in the weekly postprandial fullness symptom score for each of the last 6 weeks during the 12-week Treatment Period.

If a participant does not have individual item data for a particular symptom during any of the last 6 weeks of the 12-week Treatment Period, then the participant will not be considered a study responder for that symptom.

The proportion of responders in the RLM treatment group and placebo group for each secondary efficacy parameter will be analyzed using the analysis method as described for the V-RS primary parameter (Section 10.1.1.2).

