
Secondary
 
 • To compare the efficacy of relamorelin with placebo in participants with DG with respect to the following individual symptoms of the DGSSS: 
 • Nausea • Abdominal Pain • Postprandial fullness • Bloating • To compare the safety of relamorelin with placebo in participants with DG 	
Secondary
 
 • Individual Symptom (ie, nausea, abdominal pain, postprandial fullness, and bloating) Responder, defined as a participant with at least a 2-point decrease in the change from baseline on the weekly average of the symptom severity (at its worst) during each of the last 6 weeks of the 12-week Treatment Period • AEs, clinical laboratory values, vital signs, ECGs, HbA1c, and anti-relamorelin antibodies

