5.1. Overall Design

- Global, multicenter, randomized, double-blind, placebo-controlled, parallel-group
- Treatment Groups: Relamorelin 10 µg or placebo, twice daily, SC
- Study Duration: Up to 18 weeks, including a 12-week Treatment Period
- Study Periods: A Screening Period of up to 4 weeks, a 2-week Run-in Period, and a 12-week Treatment Period as follows:
 - Run-in Period: Participants who meet initial study entry criteria during the Screening Period will enter a 2-week placebo Run-in Period, during which they will self-administer single-blind placebo twice daily, SC. Using an electronic hand-held device, participants will report their symptoms via the Diabetic Gastroparesis Symptom Severity Diary (DGSSD) as well as their ██████████ compliance, and use of rescue medication.
 - 12-week Treatment Period: Participants who meet entry criteria at the end of the Run-in Period, will be randomized 1:1 to blinded treatment with relamorelin 10 µg or placebo. Participants will continue to use the electronic hand-held device for reporting of their symptoms via the DGSSD as well as their ██████████ compliance, and use of rescue medication.

See [Figure 2](#) for Study Schematic

Relamorelin

Figure 2: RLM-MD-02 Study Schematic

Relamorelin

Study Population:

- Screening: Males and females aged 18 years and older; T1DM or T2DM with controlled and stable blood glucose levels and HbA1c \leq 11%; symptoms suggestive of DG for at least 3 months, with mechanical obstruction of the gastrointestinal (GI) tract as the cause of symptoms having been ruled out; history of at least 2 vomiting episodes.
- During the Run-in Period: At least 1 vomiting episode and delayed GE by gastric emptying breath test (GEBT)
- After Run-in Period: Evidence of compliance during the Run-in Period with the use of the electronic hand-held device for entry of data, with twice daily SC injections of the study treatment, no treatment with GI promotility agents during the Run-in Period, at least 1 vomiting episode reported during the 2-week Run-in Period; and a score of \geq 16 for the average of the daily DGSSS assessments measured during the Run-in Period.

For studies conducted at US (IND) sites and non-US (non-IND) sites, data from IND and non-IND study sites will be pooled together for analysis.

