10.3.1. Key Statistical Methodology

The methodologies defined in [Table 10-2](#) apply as specified to individual endpoints defined in this protocol. All statistical tests will be 2-sided hypothesis tests performed at the 5% level of significance for main effects. All CIs will be 2-sided 95% CIs, unless stated otherwise.

Table 10-2: Statistical Methodology

Methodology	Description
Categorical counts	
 Number of participants in individual categories 
 Participants with ≥ 1 qualifying event counted once per individual category
Categorical descriptives	
 Number and percentage of participants in individual categories 
 Participants with ≥ 1 qualifying event counted once per individual category N1 if percentage denominator \neq number of participants in the population (standard percentage denominator) 
 N1 = participants with nonmissing baseline value
Event descriptives	
 Number and percentage of events in individual categories 
 Events counted individually for each instance Percentage denominator = total number of events
Continuous descriptives	
 N1, mean, SD, median, minimum, maximum N1 = participants with nonmissing value
CFB descriptives	
 Continuous descriptives for baseline, postbaseline, and change from baseline (CFB) values N1 = participants with nonmissing values at both baseline and the specified postbaseline analysis visit
Responder	
 Categorical descriptives for responders and nonresponders 
 Nonresponders include: 
 Participants who do not meet responder criteria Participants with no postbaseline values Risk differences and Wald CIs vs [placebo/active comparator] Estimates derived from Cochran-Mantel-Haenszel (CMH) model controlling for factors (treatment group, region) 
 Mantel-Haenszel (MH) odds ratios (ORs) and CIs vs placebo P-values comparing treatment group vs placebo N1 = all participants unless otherwise specified

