10.0 Efficacy Analyses

The efficacy analyses will be based on the mITT Population.

Most efficacy parameters will be derived from the DGSSD, a 7-item, patient-reported daily diary designed to assess the severity of 6 core signs and symptoms of DG—nausea, abdominal pain, postprandial fullness, bloating, vomiting, and early satiety—and the frequency of vomiting episodes (Appendix 1). For purposes of the analyses, weekly values will be calculated from the daily e-diary data as described in Section 16.3 of this SAP. For weeks with less than 4 days of available DGSSD data, weekly values will be set to missing.

Baseline values for parameters are derived from the DGSSD collected in the Run-in period, (ie, *Diabetic Gastroparesis Symptom Severity Score (DGSSS: sum of nausea, abdominal pain, postprandial fullness, and bloating), nausea, abdominal pain, postprandial fullness, bloating, early satiety, vomiting frequency and vomiting severity*) following the steps below:

- Weekly value for Week -2 and Week -1 will be the average value of DGSSD in the week (See the analysis week definition for Week -2 and Week -1 in Section 16.2.1);
- Baseline will be the average of the two weekly values of Week -2 and Week -1.

All statistical tests will be 2-sided hypothesis tests performed at the 5% level of significance for main effects. All confidence intervals will be 2-sided 95% confidence interval, unless stated otherwise.

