10.1.1.2 Vomiting Study Responder (V-SR)

For the primary efficacy responder parameter V-SR, the proportion of responders in the RLM group and the placebo group will be analyzed by the Cochran-Mantel-Haenszel (CMH) test controlling for geographic region. The number, percentage, and the 95% confidence interval for the percentage of Responders by treatment group, the difference in responder rates between the RLM and the placebo group and its corresponding 95% confidence interval, and the 2-sided p-value associated with the above CMH test will be presented. The Mantel-Haenszel estimate of odds ratio (RLM divided by Placebo) - controlling for geographic region- and the corresponding 95% confidence interval will also be provided.

A participant will be considered a vomiting study non-Responder (ie not a V-SR) if the weekly number of vomiting episodes is missing for any of the last 6 weeks of the 12-week Treatment Period.

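### The four symptom responder tests (H3-H6) adjust for region only; adding the item's run-in baseline would be a cheap gain in efficiency, small unless baseline is strongly prognostic

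*SAP*

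**What the plan says.** SAP 10.2 defines the nausea, abdominal pain, bloating and postprandial fullness responders and says their proportions "will be analyzed using the analysis method as described for the V-RS primary parameter" (V-RS is the vomiting responder, elsewhere V-SR). In SAP 10.1.1.2 that method has the proportions "analyzed by the Cochran-Mantel-Haenszel (CMH) test controlling for geographic region". Protocol Table 10-2 describes the same CMH approach with treatment and region as its only factors, and Table 10-3 assigns it to all four symptom endpoints. Table 10-2 also fixes the denominator: "N1 = all participants unless otherwise specified".

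Baseline is part of the endpoint. In Protocol Section 4 an individual symptom responder is "defined as a participant with at least a 2-point decrease in the change from baseline on the weekly average of the symptom severity", in each of the last six weeks. SAP 10.0 derives a run-in baseline for every diary item: "Baseline will be the average of the two weekly values of Week -2 and Week -1". The MMRM for H1 (SAP 10.1.1.1) includes baseline and its interaction with week.

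SAP 10.3 places H3-H6 under Type 1 error control, by Holm at an overall 0.05 if both primaries succeed or 0.0125 if only one does. SAP 14.0 gives power only for rejecting at least one primary hypothesis.

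**The concern.** The plan uses the item baseline to decide who responded, and uses the composite baseline to gain precision for H1, but leaves it out of the four responder tests. If improvement is roughly proportional to the starting score, a 2-point fall is easier from a higher score, so baseline predicts response and adjusting for it sharpens the comparison. If improvement is additive, baseline hardly matters.

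What is at stake is power for four tests that have none stated and that face strict thresholds. Validity is not in question. No section in the text provided plans a baseline-adjusted responder analysis, but SAP 10.4, 16.3 and Appendix 2 are not in that text.

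**Working it through.** **1. The plan's own figures.** Truncated Holm with parameter 0.5 and two hypotheses gives 0.05 × (0.5/2 + 0.5/2) = 0.025 and 0.05 × (0.5/1 + 0.5/2) = 0.0375. If only one primary is rejected, 0.05 − 0.0375 = 0.0125 passes on. All three match SAP 10.3. The first Holm step for four tests is then 0.05/4 = 0.0125 or 0.0125/4 = 0.003125.

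**2. H2 needs no help.** The inputs are 26% vs 11% and 300 per arm (SAP 14.0), with two-sided alpha 0.025 (z = 2.241).
- Pooled SE = √(2 × 0.185 × 0.815/300) = 0.0317.
- Unpooled SE = √((0.26 × 0.74 + 0.11 × 0.89)/300) = 0.0311.
- z = (0.15 − 2.241 × 0.0317)/0.0311 = 2.54, so power is 99.4%.

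Power is 97.9% with 240 per arm, and 97.3% with 300 per arm and both rates cut by 20% for dropout. This supports the stated figure of more than 90% for at least one primary.

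**3. What a given efficiency buys in one test.** With relative efficiency E, power becomes Φ(√E × (z_α + z_β) − z_α). At alpha 0.0125, z_α = 2.498.
- E = 1.03 moves 80% to Φ(1.0149 × 3.339 − 2.498) = 81.4%, and 90% to 91.0%.
- E = 1.085 moves them to 83.7% and 92.5%.

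**4. Same question by share of variance explained.** The variance is scaled by (1 − R²), where R² is the share of responder-status variance explained by baseline. For an assumed 30% vs 42% with 300 per arm at alpha 0.0125, power is 71.5% at R² = 0, 72.6% at 0.02, 74.2% at 0.05, 76.9% at 0.10 and 82.5% at 0.20. Over placebo rates of 20-40% and differences of 8-15 points, the gain is about 1 point or less at R² 0.02, 1 to 3 at 0.05, 2 to 6 at 0.10 and 3.5 to 12 at 0.20.

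**5. Full Holm procedure by simulation.** Apart from 300 per arm and features taken from the plan (entry total of at least 16, 1:1 allocation within region, 20% dropout, dropouts counted as failures), the inputs are assumptions:
- four 0-10 items with means 5.5-5.8 and correlation 0.5;
- seven regions of 242, 120, 72, 72, 48, 32 and 14;
- 2% missing baselines, also counted as failures;
- placebo response 22%; relamorelin 27%, 29.5% or 32%.

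The table gives the chance of rejecting at least one of H3-H6, CMH against the proposed score test on the same data, with 2,000 trials per cell. The Monte Carlo SE of a gain is 0.2-1.0 points.

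| AUC of baseline for response | Relative efficiency | Gain over both alphas and three effects (points) | 29.5% vs 22%, overall 0.05 |
|---|---|---|---|
| 0.54 (additive) | 1.00 | −0.4 to +0.5 | 71.1% → 71.6% |
| 0.62 | 1.03 | +0.1 to +2.1 | 72.9% → 74.5% |
| 0.65 | 1.05 | +1.1 to +2.9 | 73.3% → 75.5% |
| 0.69 | 1.09 | +1.1 to +4.6 | 75.1% → 79.6% |
| 0.76 | 1.20 | +3.5 to +11.0 | 72.9% → 81.3% |

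In 15 of the 30 cells the gain was 2.0 points or less. A repeat under the AUC 0.69 settings gave about +2.4 points, and under additive improvement none. A differently built single-item simulation at alpha 0.0125 (region-only CMH vs logistic with baseline) showed the same pattern: 71.5 vs 71.7% (R² 0.001), 69.1 vs 70.7% (0.014), 64.7 vs 67.6% (0.047) and 58.5 vs 63.3% (0.095).

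**6. Error control and the estimate.** Under the null with 5% missing baselines, familywise error for CMH and for the score test with its small-sample factor was:
- AUC 0.76: 4.8% and 5.1% at overall 0.05; 1.5% and 1.5% at 0.0125.
- AUC 0.69: 4.5% and 4.6% at overall 0.05; 1.1% and 1.3% at 0.0125.

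The standardised risk difference had variance ratios to the unadjusted estimate of 1.00 (AUC 0.54), 0.92 (0.69) and 0.85 (0.76), with 95% interval coverage of 94.8%, 95.2% and 95.1%.

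**The case against.** - **Nothing is broken.** Region-only CMH is valid and the documents agree, so this is a preference. That is true, and it is why the point is put as an efficiency gain.
- **The tests will not be run.** SAP 4.0 reports termination, withdraws the full analyses and adds only descriptive summaries. This stands: no result in the abbreviated report would change.
- **The size rests on assumptions, and half the simulated cells gain 2 points or less.** This stands. The 11-point figure needs a baseline more prognostic than anything the documents support.
- **The 1.5% familywise error at overall 0.0125 looks high.** With 14,000 trials the SE is √(0.0125 × 0.9875/14,000) = 0.09 points, so 1.5% is about 2.7 SE above nominal. CMH showed the same 1.5% on the same data. Two repeats gave 1.1% and 1.2% for CMH against 1.2% and 1.3% for the score test, so simulation noise is the likely cause. CMH is slightly more conservative, which accounts for a little of the apparent gain.
- **A region with no responders makes its logistic coefficient diverge.** It adds nothing to the score test and barely moves the correction. With the assumed regions, counting all seven gives (600 − 8)/600 = 0.9867; dropping the region of 14 gives (586 − 7)/586 = 0.9881. The SAP should still say which count applies.
- **H2 and H3-H6 would use different responder methods, and Protocol Table 10-3 assigns the CMH method.** The difference is real. SAP 17.0 is the place to record it.
- **An adjusted analysis may sit in text not provided.** The SAP abbreviations include ANCOVA and the references include a paper on nonparametric covariance analysis. This cannot be excluded.

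**Conclusion.** The point holds as an improvement to a valid analysis. Adjusting H3-H6 for the item baseline costs no data. It yields nothing if improvement is additive, between about 0 and 5 points in the chance of at least one rejection at AUC 0.62 to 0.69, and 3.5 to 11.0 points only at AUC 0.76. These sizes depend on assumed response rates, region sizes, baseline spread and prognostic strength, none of which the documents give. H2 should stay as written because its power is already about 97-99%. The recommendation applies to the inferential plan or any reuse of it, and not to the abbreviated report. Confidence is medium.

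**What to change.** In SAP 10.2, for H3-H6 only, replace the cross-reference to 10.1.1.2 with:

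1. **Test.** A score test for treatment in a logistic model with region (pooled under SAP 16.11) and the same item's baseline. Multiply the chi-square by (n − q)/n, where q is the number of parameters in the model without treatment.
2. **Regions without responders.** They contribute nothing to the test, as in CMH, so no further pooling rule is needed. State whether they count in n and q.
3. **Missing baseline.** The participant stays in as a non-responder, with the blinded mean baseline of both arms together as covariate. This keeps the Table 10-2 denominator. A baseline can be missing because "For weeks with less than 4 days of available DGSSD data, weekly values will be set to missing", but it should be uncommon, since randomisation requires "Evidence of compliance during the Run-in Period with the use of the electronic hand-held device for entry of data". With the plain score test at AUC 0.69, raising missing baselines from 0% to 5% left the gain unchanged (77.9% to 82.3%, and 74.2% to 78.5%).
4. **Estimate.** A standardised risk difference with an influence-function standard error, so that the effect stays marginal.
5. **Supportive.** The region-stratified CMH test and Mantel-Haenszel odds ratio.

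Do not stratify CMH by region and baseline tertile instead: when baseline was not prognostic that lost about 1 point (70.3% vs 71.5% at alpha 0.0125).

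Record the departure from Protocol Table 10-2 in SAP 17.0, which now lists no changes. Leave H2, its multiple imputation (SAP 10.1.2.1) and the rescue-medication repeat (SAP 10.6) alone.

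The cost is one paragraph, one log entry and one program run on four endpoints. The downsides are a conditional odds ratio if the model's own is reported, occasional disagreement between the p-value and the risk-difference interval, and a missing-baseline rule that CMH does not need.

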10.3 Multiple Comparisons Procedure

[figure not shown]
The overall study Type 1 error will be controlled for the 6 efficacy parameters, 2 primary and 4 secondary parameters, as defined above (Sections 10.1 and 10.2). To control the overall type-1 error rate of the study, the hypotheses of interest will be grouped into the following two families:

[figure not shown]
- Family 1:
 - Hypothesis H1: Comparison of relamorelin vs. placebo in change from baseline to Week 12 in the Weekly DGSSS
 - Hypothesis H2: Comparison of relamorelin vs. placebo in proportion of participants who achieved responder status for V-SR
- Family 2:
 - Hypotheses H3-H6: Comparison of relamorelin vs. placebo in the response rates of the individual symptoms comprising DGSSS (ie, nausea, abdominal pain, bloating and postprandial fullness)

[figure not shown]
Then, multiple testing will be performed in two steps ([Dmitrienko et. al., 2008](#)) as follows:

- Step 1: Treatment comparisons to placebo in change from baseline to Week 12 in the Weekly DGSSS and vomiting response rates will be performed using the truncated Holm test at alpha=0.05. A truncation parameter of 0.5 will be used. According to this procedure, the smallest and largest p-values will be compared to the critical values of 0.025 and 0.0375 respectively in a step-down manner (i.e. starting with the smallest p-value and stopping the testing with the first non-rejected hypothesis).
- Step 2: If any of the comparisons at Step 1 is significant, the treatment comparisons to placebo in the individual symptoms response rates will be performed using the regular Holm test at a level alpha that depends on the unused alpha from Step 1 as follows:
 - 1) If both H1 and H2 are both rejected in Step 1, H3-H6 will be tested using an overall alpha=0.05
 - 2) If only one of H1 and H2 is rejected in Step 1, H3-H6 will be tested using an overall alpha=0.0125
 - 3) If none of H1 and H2 is rejected, the testing procedure will be stopped and H3-H6 are not tested

According to the above procedure, the k-th ordered p-value in 1) and 2) in Step 2 will be compared to the critical values of $\alpha/(4-k+1)$, $k=1, \dots, 4$, in a step-down manner (i.e. starting with the smallest p-value and stopping the testing with the first non-rejected hypothesis), where α is the significance level from Step 2.

10.5 Subgroup Analyses

The analyses of the primary parameters will be presented by selected subgroups as below:

- Diabetes type (Type I / Type II)
- Baseline HbA1c (<9% vs >=9%)
- Gender

These subgroup analyses will be contingent on the presence of an adequate number of participants in each subgroup. Only descriptive summary in the study level will be provided. Statistical comparisons within subgroups based on the pooled data will be performed separately in the integrated efficacy analysis.

For the analyses of diabetes subgroups, participants will be classified as having Type I Diabetes Mellitus if “Type 1 Diabetes Mellitus” is selected as their answer on the Diabetic Gastroparesis and Diabetes Mellitus History eCRF page and/or if the results of T1DM antibody tests at the baseline visit (V3) include at least one positive result for the 3 T1DM antibodies being tested (Anti-GAD Antibody ≥ 5.00 U/mL = positive, IA2 Autoantibody ≥ 7.50 U/mL = positive, Zn-T8 Antibody ≥ 15 U/mL = positive). Participants with history of Type 2 Diabetes Mellitus and no positive result on any of the 3 different T1DM antibodies will be classified as Type II Diabetes Mellitus.

10.6 Rescue Medication

The proportion of participants who took any rescue medication (RM) will be presented by week and treatment, and by treatment for the entire duration of the 12-week double-blind treatment period. Rescue medication use will also be summarized as percent of days with RM use, calculated for each participant as the number of days with RM over the number of days in the entire double-blind treatment period.

To assess the impact of rescue medication use on the assessment of effectiveness, the analyses for the primary parameters will be repeated but with the weekly DGSS and vomiting frequency values considered missing following use of RM for two days or more during a week. As a result, participants with two or more than two days of RM use during a week for one or more weeks during the last 6 weeks of treatment will not be considered as Vomiting Study Responders.

11.0 Safety Analyses

The safety analysis will be performed using the Safety Population. The safety parameters will include adverse events (AEs), clinical laboratory, electrocardiogram, and vital sign parameters.

For each safety parameter of the clinical laboratory, electrocardiogram, and vital sign parameters, the last nonmissing safety assessment before the first dose of double-blind investigational product will be used as the baseline for all analyses of that safety parameter. Continuous variables will be summarized by number of participants and mean, SD, median, Q1, Q3, minimum, and maximum values. Categorical variables will be summarized by number and percentage of participants.

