With respect to laboratory findings, in some participants glycemic control may have been negatively affected by the introduction of relamorelin. There were trends in increasing haemoglobin A1c (HbA1c) values after the initiation of relamorelin, which increased slightly after approximately 8 weeks, and dose-related trends in fasting hyperglycemia. Otherwise, no clinically relevant abnormalities were seen for other laboratory tests, including liver function tests, electrocardiograms (ECGs), physical examination findings, and injection site reactions; anti-drug antibodies (ADAs) were not found.

A detailed description of the chemistry, pharmacology, efficacy, and safety of relamorelin is provided in the investigator's brochure (Relamorelin Investigator's Brochure).

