3.3. Benefit/Risk Assessment

Based on information about relamorelin obtained to date, the benefits of study participation are expected to include accelerated GE and clinically meaningful improvement in the symptoms of DG, including nausea, abdominal pain, postprandial fullness, bloating, vomiting frequency, early satiety, and vomiting severity. A potential risk of treatment is worsening of glycemic control, including the possibility of diabetic ketoacidosis occurring. However, preventive measures, including special laboratory assessments to allow early recognition by investigators and participants of rising glucose levels, are being included in this protocol so that early remedial action (eg, adjustment of medication and diet) may be taken to minimize increase in glucose levels; this might increase the incidence of hypoglycemic reactions, especially in participants with T1DM. See Section 5 Study Design for details of study procedures, dose, and study design justification.

More detailed information about the known and expected benefits and risks and reasonably expected AEs associated with relamorelin are provided in the investigator's brochure (Relamorelin Investigator's Brochure); information about the investigational directions for use (DFU) for the pen injector, the device that will be used to administer study treatment are also provided.

Relamorelin

4. Objectives and Endpoints

Objectives	Endpoints

Primary
 
 • To compare the efficacy of relamorelin with placebo in participants with DG with respect to a composite of the following core signs and symptoms of DG: 
 • Nausea • Abdominal pain • Postprandial fullness • Bloating • To compare the efficacy of relamorelin with placebo in participants with DG with respect to vomiting frequency 	
Primary
 
 • Change from Baseline to Week 12 in the weekly DGSSS. Baseline is defined as the average of the 2 weekly DGSSS from the 2-week placebo Run-in Period. • Vomiting Responder, defined as a participant with zero weekly vomiting episodes during each of the last 6 weeks of the 12-week Treatment Period

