5.5. Justification for Dose

[figure not shown]
Study RM-131-009 was a 12-week Phase 2b, randomized, double-blind, placebo-controlled, parallel group study to evaluate the safety and efficacy of relamorelin in diabetic participants with moderate to severe DG. The doses included within the study were 10 µg BID, 30 µg BID, and 100 µg BID. In general, all doses tested within RM-131-009 appeared to demonstrate meaningful reductions in overall DG symptom scores including vomiting episodes, with acceptable safety and tolerability. The frequency of vomiting episodes was reduced from baseline over the 12-week Treatment Period to a similar extent for participants who received the 3 doses of relamorelin and placebo. Based upon the observed dose response of change-from-baseline symptom scores collected daily over the course of 12 weeks using the DGSSD, the 30 µg BID, and 100 µg BID doses demonstrated apparent maximal symptom score improvements, while the 10 µg BID dose achieved near maximal improvements. Of note, the twice-a-day regimen of relamorelin appears to be necessary for effective symptom relief; the 10 µg once daily study treatment did not demonstrate significant improvement in symptom relief compared to placebo after 28 days of dosing in Study RM-131-004.

Review of the safety laboratory data collected in RM-131-009 revealed an apparent dose-related increase in HbA1c values. Although the variability in HbA1c response was high across all treatments, the 30 µg BID and 100 µg BID doses demonstrated apparent maximal changes in HbA1c values, while the 10 µg BID dose resulted in an approximately half-maximal increase

██████████
Relamorelin

10. Able to provide written informed consent (IC) prior to any study procedures and willing and able to comply with study procedures (as defined in Appendix 3)

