11.5 Study Specific Assessments

Study-specific assessments (HbA1c, IGF-1 etc.) are summarized as part of the overall clinical laboratory assessments.

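### The objective is to compare safety with placebo, but no between-arm estimate or confidence interval is prespecified for HbA1c or for glycaemic events of special interest

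*SAP*

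**What the plan says.** Protocol Section 4 and SAP Section 5.0 set the same secondary objective: "To compare the safety of relamorelin with placebo in participants with DG". The endpoints listed against it in the protocol are "AEs, clinical laboratory values, vital signs, ECGs, HbA1c, and anti-relamorelin antibodies".

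The protocol treats glycaemia as more than a routine laboratory matter. Section 3.3 states: "A potential risk of treatment is worsening of glycemic control, including the possibility of diabetic ketoacidosis occurring". On the Phase 2b data, Section 3.2 reports: "There were trends in increasing haemoglobin A1c (HbA1c) values after the initiation of relamorelin". Section 5.5 describes an apparent dose-related rise in which "the 10 µg BID dose resulted in an approximately half-maximal increase", with the caveat "Although the variability in HbA1c response was high across all treatments".

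Protocol Section 10.3.3 foresees safety summaries such as descriptives and shift tables and leaves full definition to the SAP. The SAP then provides:

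- **Section 11.0:** "Continuous variables will be summarized by number of participants and mean, SD, median, Q1, Q3, minimum, and maximum values".
- **Section 11.5:** "Study-specific assessments (HbA1c, IGF-1 etc.) are summarized as part of the overall clinical laboratory assessments".
- **Section 11.2 and Table 11.2-1:** values and changes from baseline by arm and time point, the number and percentage per arm with an HbA1c rise of at least 0.5% and of at least 1%, and baseline-to-end-of-trial shift tables by arm.
- **Section 11.1.1:** per-arm number and percentage with hyperglycaemia and hypoglycaemia events of special interest.
- **Section 16.1:** an end-of-trial row in the safety tables.

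**The concern.** The objective is a comparison, and none of these outputs is one. For the outcome that the sponsor itself singled out, the report would show two columns and leave the contrast to the reader. High variability in HbA1c response, which the protocol acknowledges, is the setting in which comparing two means by eye is least reliable.

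Two design features add to this. Randomization is stratified by geographic region only (Protocol Section 7.3), so baseline HbA1c can differ between arms by chance, and the plan has no adjusted contrast to absorb that. Adjustment of diabetes medication during the study is encouraged (Protocol Section 7.7.2), which may shrink a difference in HbA1c. The range of differences compatible with the data is then more informative than two point summaries.

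At stake is whether the report carries an agreed, prespecified statement of the size of the HbA1c difference and of what the data exclude.

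**Working it through.** **What is planned, set against the primary endpoint**

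| Element | DGSSS change (SAP 10.1.1.1) | HbA1c change (SAP 11.0, 11.2, 11.5) |
|---|---|---|
| Per-arm summary | yes | yes |
| Between-arm difference | yes | no |
| 95% CI for the difference | yes | no |
| Baseline as covariate | yes | no |

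Baseline HbA1c is used elsewhere: in change scores, in the two rise thresholds, in shift tables, and as a subgroup factor (below 9% against 9% or more) in SAP Sections 10.5 and 11.7.

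**Inputs for size**

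The documents give no precision figure for HbA1c, so there is none to reproduce. From the documents: 300 randomized per arm and 20% dropout by Week 12, so 300 × (1 − 0.20) = 240 per arm, which matches the planned completers. Assumed, because not in the documents: HbA1c SD 1.2 to 1.5 percentage points, and correlation r between baseline and Week 12 of 0.6 to 0.8.

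**Formulas**

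- Change score, unadjusted: s = SD × √(2(1 − r))
- Adjusted for baseline: s = SD × √(1 − r²)
- 95% CI half-width = 1.96 × s × √(2/240), where √(2/240) = 0.0913

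**Results**

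| Case | s, unadjusted | Half-width | s, adjusted | Half-width |
|---|---|---|---|---|
| SD 1.2, r = 0.8 | 0.759 | 0.14 | 0.720 | 0.13 |
| SD 1.5, r = 0.6 | 1.342 | 0.24 | 1.200 | 0.21 |

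The ratio of adjusted to unadjusted standard errors is √((1 + r)/2): 0.894, 0.922 and 0.949 for r = 0.6, 0.7 and 0.8. These are reductions of 10.6%, 7.8% and 5.1%.

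With wider assumptions (SD 1.0 to 1.5, r = 0.5 to 0.9) the half-widths are 0.08 to 0.27 unadjusted and 0.08 to 0.23 adjusted.

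**Binary outcomes, with assumed rates**

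- HbA1c rise of at least 0.5%, 240 per arm: at 20% in both arms the half-width is 1.96 × √(2 × 0.20 × 0.80/240) = 7.2 percentage points. At 40% against 30% it is 8.5 points.
- A glycaemic event of special interest at 10% against 6%, 300 per arm: the difference is 4 points and the half-width is 1.96 × √((0.10 × 0.90 + 0.06 × 0.94)/300) = 4.3 points. The interval runs from about −0.3 to 8.3 points.

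**The case against.** The case against is substantial, and much of it stands.

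- **No conflict with the protocol.** Section 10.3.3 foresees descriptive safety analysis, and the SAP delivers it. A reader might infer that the SAP departs from the protocol; it does not. The gap is between the comparative objective and the output chosen for it.
- **Baseline is used.** A reader might infer that baseline HbA1c goes unused. Change scores, rise thresholds, shift tables and subgroups all need it. It is absent only as a covariate in a between-arm comparison.
- **Early leavers are not simply lost.** By-visit means invite that inference, but Section 16.1 adds a row for the final or termination visit, Section 16.4 takes the last post-baseline value when end-of-trial assessments are repeated or unscheduled, and all post-baseline values count towards the thresholds. The end-of-trial row does mix follow-up times and still gives no contrast.
- **The effect could still be sized.** It is too strong to say that the report could not show how large the difference is. The planned n, mean and SD of change give an unadjusted interval, and the planned counts give crude risk differences. What is missing is prespecification and adjustment.
- **The precision gain is small.** It is about 0.01 to 0.03 points of half-width under the assumed range, and the inputs are assumptions.
- **The HbA1c visit schedule is redacted** in the supplied text, so a repeated-measures model may or may not be feasible.
- **Termination.** SAP Section 4.0 says that the full analyses no longer apply and that only an abbreviated report will be produced. The appendix that outlines it is not in the supplied text.

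The core point survives: no between-arm estimate or interval for HbA1c or the glycaemic events appears in the SAP sections available.

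**Conclusion.** The point holds as a gap in prespecified estimation. The safety objective is comparative, HbA1c is a named endpoint with a prior dose-related signal, and the SAP plans only per-arm output for it and for glycaemic events of special interest.

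Under the assumptions shown, the planned sample would have located the HbA1c difference to within about 0.13 to 0.24 points, depending on SD, correlation and adjustment. Most of the benefit comes from stating an estimate and interval in advance; baseline adjustment is a modest extra. The half-widths use the design target of 240 per arm. The number with HbA1c data at termination is not given, and for n per arm they scale by √(240/n).

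The plan's wording supports calling glycaemic worsening a potential risk with an apparent Phase 2b signal. It does not support calling it an established harm. Practical reach is limited by the abbreviated report, although the same SAP also governs the identically designed RLM-MD-01.

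**What to change.** In SAP Sections 11.2 and 11.5, and in the abbreviated-report outline if the data allow:

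1. Add the between-arm difference in HbA1c change to Week 12 with a 95% CI, adjusted for baseline HbA1c and region. Use the repeated-measures form of Section 10.1.1.1 if there are at least two post-baseline HbA1c visits, and ANCOVA otherwise.
2. Add risk differences with 95% CIs for HbA1c rises of at least 0.5% and at least 1%, and for the hyperglycaemia and hypoglycaemia events of special interest.
3. Label all of these as estimation, with no p-values.
4. State that the HbA1c difference is the one seen under the adjustment of diabetes medication that the protocol permits.

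The cost is SAP wording and two or three tables. No new data are needed, and the methods are already in Protocol Table 10-2 (adjusted mean differences with intervals, and risk differences with Wald intervals) and SAP Section 10.1.1.1. The downside is a few intervals without multiplicity control, which the estimation label makes plain.
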